6 STUDY INTERVENTION(S) AND CONCOMITANT THERAPY

Study intervention is defined as any investigational intervention(s), marketed product(s), intended to be administered to a study participant according to the study protocol.

6.1 STUDY INTERVENTION(S) ADMINISTERED

Participants will receive study treatment until PD, unacceptable toxicity, other permanent discontinuation criteria as described in [Section 7](#), or completion of Cycle 35 (if applicable).

6.1.1 Investigational medicinal product (IMP)

Details of each SAR444245 are shown in [Table 2](#).

For a regional or national emergency declared by a governmental agency that results in travel restrictions, confinement, or restricted site access, contingency measures are included in [Section 10.9](#).

Preparation and administration of SAR444245 are detailed in the pharmacy manual. Hydration is required for SAR444245 infusions. Details are provided in [Section 6.1.3](#).

Table 2 - Overview of IMP administered

Intervention name	SAR444245
Type	Biological
Dose formulation	Concentrate for solution for infusion
Unit dose strength(s)	2.0 mg/mL
Dosage level(s)^a	24 µg/kg Q3W
Route of administration	IV infusion
Use	Experimental
IMP or NIMP	IMP
Packaging and labeling	Supplied in a single-dose vial in a treatment box. Each vial contains 2 mg/mL with an extractable volume of 1 mL. Each vial and treatment box will be labeled as required per country requirement.
Current/Former name(s) or alias(es)	NA

^a The total dose will be calculated based on the weight on the day of the infusion or the most recent weight assuming it was assessed in a reasonable time frame according to Investigator assessment. Study sites should make every effort to measure body weight as close to the infusion day as possible considering the variability of local process from site to site. If the infusion is prepared with the most recent weight assessed in a reasonable time frame, the participant must still be weighed on D1 of each cycle, and the weight recorded in the e-CRF. Study sites should make every effort to target infusion timing to be as close to 30 minutes as possible. However, given the variability of infusion pumps from site to site, a window of -5 minutes and +10 minutes is permitted.

6.1.2 Non-investigational medicinal products

Non-investigational medicinal products include the premedication administered for SAR444245.

6.1.2.1 *Premedication for SAR444245*

[figure not shown]
All participants will receive the following premedication to prevent or reduce the acute effect of IRR or flu-like symptoms, 30 to 60 minutes prior to SAR444245 infusion (no longer than 60 minutes) for the first 4 cycles:

[figure not shown]
- Acetaminophen (paracetamol) 650 to 1000 mg (IV or PO) (or equivalent), and then optionally thereafter as needed.
- Diphenhydramine 25 to 50 mg IV or PO (or equivalent, eg, cetirizine, promethazine, dexchlorpheniramine, according to local approval and availability), and then optionally thereafter as needed.

SAR444245 premedication may be optional after 4 cycles:

- For a participant who has no IRR for the first 4 cycles, premedication for the subsequent infusions is optional at the Investigator's discretion. However, if during the subsequent infusions without premedication the participant experiences an IRR (any grade), premedication must be restarted for all subsequent infusions.
- If a participant develops an IRR Grade <2 during their first cycle only and then experiences no further IRRs during their next 3 cycles the Investigator may consider omitting premedication for Cycle 5. If no IRR is observed during Cycle 5 without premedication, premedication is optional for the subsequent cycles at the Investigator's discretion. However, if during Cycle 5 without premedication the participant experiences an IRR (any grade), premedication must be restarted for all subsequent cycles.

6.1.3 Hydration guidelines for SAR444245 administration

6.1.4 Readiness for treatment of severe cytokine release syndrome

Doses of tocilizumab or alternative therapies per site practice in CRS management should be available at the site at all times in the event that a participant requires rapid intervention for the treatment of severe CRS. Please refer to Section 6.5 of individual substudies for detailed guidelines for the management of CRS.

6.2 PREPARATION/HANDLING/STORAGE/ACCOUNTABILITY

1. The Investigator or designee must confirm appropriate temperature conditions have been maintained during transit for all study intervention received and any discrepancies are reported and resolved before use of the study intervention.
2. Only participants enrolled in the study may receive study intervention and only authorized site staff may supply or administer study intervention. All study intervention must be stored in a secure, environmentally controlled, and monitored (manual or automated) area in accordance with the labeled storage conditions with access limited to the Investigator and authorized site staff.
3. The Investigator, institution, or the head of the medical institution (where applicable) is responsible for study intervention accountability, reconciliation, and record maintenance (ie, receipt, reconciliation, and final disposition records).

Any quality issue noticed with the receipt or use of an IMP (deficiency in condition, appearance, pertaining documentation, labeling, expiration date, etc) must be promptly notified to the Sponsor. Some deficiencies may be recorded through a complaint procedure (see [Section 8.3.9](#)).

A potential defect in the quality of IMP may be subject to initiation of a recall procedure by the Sponsor. In this case, the Investigator will be responsible for promptly addressing any request made by the Sponsor, in order to recall the IMP and eliminate potential hazards.

Under no circumstances will the Investigator supply IMP to a third party, allow the IMP to be used other than as directed by this clinical trial protocol, or dispose of IMP in any other manner.

Treatment preparation and administration (including compatible materials) will be further detailed in the pharmacy manual.

6.3 MEASURES TO MINIMIZE BIAS: RANDOMIZATION AND BLINDING

Not applicable.

6.4 STUDY INTERVENTION COMPLIANCE

Participants must be dosed at the site and will receive IMP directly from the Investigator or designee, under medical supervision. The person responsible for drug dispensing is required to maintain adequate records of the IMP administration. These records include the date the IMP components are received from the Sponsor, dispensed to the participant and destroyed or returned to the Sponsor. The packaging batch number and the treatment number on the vial must be recorded on the drug accountability form. The date and time of each dose administered in the clinic will be recorded in the source documents and recorded in the e-CRF. The dose of study intervention and study participant identification will be confirmed at the time of dosing by a member of the study site staff other than the person administering the study intervention.

6.5 DOSE MODIFICATION

Please see respective substudy protocols.

6.6 CONTINUED ACCESS TO INTERVENTION AFTER THE END OF THE STUDY

There will be no intervention beyond the end of the study.

6.7 TREATMENT OF OVERDOSE

There is no specific antidote for overdose with SAR444245.

If overdose occurs (see [Section 8.3.8](#) for definitions), symptomatic management is indicated.

Treatment of overdose should consist of general supportive care with aggressive fluid management, if clinically indicated.

Procedures for treating symptoms and complications of irAEs are provided in the individual substudies.

In the event of an overdose, the Investigator should:

1. Contact the Sponsor immediately.
2. Closely monitor the participant for any AE/SAE and laboratory abnormalities until study intervention can no longer be detected systemically (at least 90 days).
3. Obtain a plasma sample for PK analysis right after the overdose event is identified (only if an overdose is identified within 5 days from start of overdose infusion).
4. Document appropriately in the e-CRF.

Decisions regarding dose interruptions or modifications will be made by the Investigator in consultation with the Sponsor based on the clinical evaluation of the participant.

6.8 CONCOMITANT THERAPY

Any medication or vaccine (including over-the-counter [OTC] or prescription medicines, vitamins, and/or herbal supplements, or other specific categories of interest) that the participant is receiving at the time of enrollment or receives during the study must be recorded along with:

- Reason for use.
- Dates of administration including start and end dates.

The Sponsor should be contacted if there are any questions regarding concomitant or prior therapy.

Medications or vaccinations specifically prohibited in the exclusion criteria are not allowed during the ongoing trial. If there is a clinical indication for any medication or vaccination specifically prohibited during the trial, discontinuation from study intervention may be required. The Investigator is to discuss prohibited medication/vaccination with the Sponsor. The final decision on any supportive therapy or vaccination rests with the Investigator and/or the participant's primary physician. However, the decision to continue the participant on trial therapy schedule requires the mutual agreement of the Investigator, the Sponsor and the participant.

6.8.1 Acceptable concomitant medications

All treatments that the Investigator considers necessary for a participant's welfare may be administered at the discretion of the Investigator in keeping with the community standards of medical care. All concomitant medication will be recorded on the electronic case report form (e-CRF) including all prescription, OTC, herbal supplements, and IV medications and fluids. If changes occur during the trial period, documentation of route, and date will also be included on the e-CRF.

Palliative and supportive care is permitted during the course of the trial for underlying medical conditions and management of symptoms. Surgery or radiotherapy for tumor control is not permitted during the study; however, radiotherapy or procedures for symptom management is allowed after discussion with and approval by the Sponsor.

All concomitant medications received within 28 days before the first dose of trial treatment through the Follow-up Visit should be recorded.

Colony-Stimulating Factors

Routine use of colony-stimulating factors (CSFs) is not permitted. American Society of Clinical Oncology guidelines for use of CSFs should be followed ([25](#)).

6.8.2 Prohibited concomitant medications

Participants are prohibited from receiving the following therapies during the Screening and Treatment Period of this trial:

- Antineoplastic systemic chemotherapy or biological therapy not specified in this protocol.
- Immunotherapy not specified in this protocol.
- Investigational agents other than specified in this protocol.
- Radiotherapy for tumor control (please refer to [Section 6.8.1](#) for allowed radiotherapy).
- Live or live attenuated virus vaccines within 28 days prior to the first dose of trial treatment and while participating in the trial. Examples of live-virus vaccines include, but are not limited to, the following: measles, mumps, rubella, chickenpox, yellow fever, seasonal flu (seasonal flu vaccines that do not contain live virus are permitted), nasal H1N1 flu, rabies, Bacillus Calmette-Guérin (BCG), and typhoid.
- Systemic glucocorticoids and other immunosuppressive therapies such as anti-TNF, anti-IL6, etc, except for:
 - Treatment of AEs when indicated (irAE, CRS, ICANS, IRR, see Section 6.5 of individual substudies),
 - Treatment of any life-threatening emergency,
 - Physiologic replacement as long as they are not being administered for immunosuppressive intent, and
 - A brief course (≤ 7 days) of systemic corticosteroid for prophylaxis (eg, contrast dye allergy) or for the treatment of non-autoimmune conditions (eg, delayed-type hypersensitivity reactions caused by contact allergen).

Participants who, in the assessment by the Investigator, require the use of any of the aforementioned treatments for clinical management should be removed from the trial. Participants may receive other medications that the Investigator deems to be medically necessary.

The exclusion criteria describe other medications which are prohibited in this trial.

There are no prohibited therapies during the Observation and Survival Follow-up Period.

For withholding antihypertensive medications as part of hydration guidelines, please refer to [Section 6.1.3](#).

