7 DISCONTINUATION OF STUDY INTERVENTION AND PARTICIPANT DISCONTINUATION/WITHDRAWAL

7.1 DISCONTINUATION OF STUDY INTERVENTION

7.1.1 Permanent discontinuation

Study intervention should be permanently discontinued in any of the following cases:

- At the participant's request, at any time and irrespective of the reason (consent's withdrawal), or at the request of their legally authorized representative (if allowed by local regulations). "Legally authorized representative" is considered to be an individual or judicial or other body authorized under applicable law to consent on behalf of a prospective participant to the patient's participation in the procedure(s) involved in the research.
- If, in the Investigator's opinion, continuation of the study treatment would be detrimental to the participant's wellbeing, such as:
 - Unacceptable AE.
 - Documented disease progression.
 - Poor compliance to the study protocol.
 - Completion of 35 cycles when applicable.
 - Other, such as concurrent illness, that prevents further administration of study intervention, or that in the Investigator's opinion, in the best interest of the participant.
- In case of pregnancy occurrence.

If study intervention is permanently discontinued, the participant will remain in the study to be evaluated for serial tumor assessment if permanent discontinuation is not due to PD, for safety assessment as per SoA ([Section 1.3](#)) and until resolution or stabilization of AE, and any other assessment as per SoA. Data to be collected at the time of discontinuation of study intervention and follow-up and for any further evaluations that need to be completed are reported in the SoA.

7.1.1.1 ***Unacceptable adverse events leading to permanent intervention discontinuation***

Discontinuation of study intervention for abnormal liver function should be considered by the Investigator when a participant meets one of the conditions outlined in the dose modification and toxicity management guidelines (see individual substudy protocols), or if the Investigator believes that it is in best interest of the participant.

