If a clinically significant finding is identified (including, but not limited to changes from baseline in QT interval corrected using Fridericia's formula [QTcF]) after enrollment, the Investigator or qualified designee will determine if the participant can continue in the study and if any change in participant management is needed. This review of the ECG printed at the time of collection must be documented. Any new clinically relevant finding should be reported as an AE.

Any potentially clinically significant abnormal laboratory value or ECG parameter will be immediately rechecked for confirmation and repeated after 24 hours to document evolution before making a decision of permanent intervention discontinuation for the concerned participant.

Decision criteria for discontinuation following immune-mediated AEs are described in Section 6.5 of individual substudies (Guidelines for the management of IRR, CRS, ICANS, VLS).

If participants are clinically stable, and possibly deriving clinical benefit from therapy with minimal toxicity, they will be maintained on treatment.

See the SoA for data to be collected at the time of intervention discontinuation and follow-up and for any further evaluations that need to be completed.

Handling of participants after permanent intervention discontinuation

Participants will be followed-up according to the study procedures specified in this protocol up to the scheduled date of study completion, or up to recovery or stabilization of any AE to be followed-up as specified in this protocol, whichever comes last.

If possible, and after the permanent intervention discontinuation, the participants will be assessed using the procedure normally planned for the last dosing day with the IMP including a pharmacokinetics sample, if appropriate. Tumor assessment should be repeated if not done at the last cycle.

All cases of permanent intervention discontinuation must be recorded by the Investigator in the appropriate pages of the e-CRF when considered as confirmed.

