7.2 PARTICIPANT DISCONTINUATION/WITHDRAWAL FROM THE STUDY

- A participant may withdraw from the study at any time at his/her own request, or may be withdrawn at any time at the discretion of the Investigator for safety, behavioral, or compliance reasons. This is expected to be uncommon.
- At the time of discontinuing from the study, see SoA for data to be collected at the time of study discontinuation and follow-up and for any further evaluations that need to be completed.
- The participant will be permanently discontinued both from the study intervention and from the study at that time.
- If the participant withdraws consent for disclosure of future information, the Sponsor may retain and continue to use any data collected before such a withdrawal of consent.
- If a participant withdraws from the study, he/she may request destruction of any samples taken and not tested, and the Investigator must document this in the site study records.

If participants no longer wish to take the IMP, they will be encouraged to remain in the study.

The Investigators should discuss with them key visits to attend. The value of all their study data collected during their continued involvement will be emphasized as important to the public health value of the study.

Participants who withdraw from the study intervention should be explicitly asked about the contribution of possible AEs to their decision, and any AE information elicited must be documented.

All study withdrawals should be recorded by the Investigator in the appropriate screens of the e-CRF and in the participant's medical records. In the medical record, at least the date of the withdrawal and the reason should be documented.

In addition, a participant may withdraw his/her consent to stop participating in the study. Withdrawal of consent for intervention should be distinguished from withdrawal of consent for follow-up visits and from withdrawal of consent for non-participant contact follow-up, eg, medical record checks. The site should document any case of withdrawal of consent.

Participants who have withdrawn from the study cannot be re-included in the study. Their inclusion and intervention numbers must not be reused.

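### Section 6.8.2 takes participants who need a prohibited treatment out of the trial, while sections 6.8, 7.1.1 and 8.3.1 keep them in follow-up

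*Protocol*

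**What the plan says.** Section 6.8.2 of the master protocol lists treatments prohibited during the Screening and Treatment Period: other anticancer drugs, immunotherapy, investigational agents, radiotherapy for tumor control, live vaccines, and systemic glucocorticoids or other immunosuppressants with stated exemptions. Participants who, in the Investigator's assessment, "require the use of any of the aforementioned treatments for clinical management should be removed from the trial". The same section then states that nothing is prohibited once the participant is in the Observation or Survival Follow-up Period.

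Other sections treat the same or overlapping situations differently:

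- **6.8**, on a clinical indication for a prohibited medication or vaccine: "discontinuation from study intervention may be required". It allows for staying on treatment, since "the decision to continue the participant on trial therapy schedule requires the mutual agreement of the Investigator, the Sponsor and the participant".
- **7.1.1**: "If study intervention is permanently discontinued, the participant will remain in the study to be evaluated for serial tumor assessment", provided the stop was not for progression, and for safety assessment in any case. Its text on handling after a permanent stop adds: "Participants will be followed-up according to the study procedures specified in this protocol up to the scheduled date of study completion", or until adverse events recover or stabilize if that is later.
- **1.1 and 4.1**: a participant who starts another anticancer therapy moves to survival phone follow-up.
- **8.3.1**: SAEs and AESIs are collected until 90 days after the last dose, with no exception for a new therapy. Substudy 01, section 8.3.1, does the same for immune-related events in Cohort A and says explicitly that a new anticancer therapy makes no difference.
- **7.2**: a participant "may be withdrawn at any time at the discretion of the Investigator for safety, behavioral, or compliance reasons", and then "The participant will be permanently discontinued both from the study intervention and from the study at that time". Section 7.1.1 lists unacceptable adverse events and "Poor compliance to the study protocol" as reasons to stop the intervention only.

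**The concern.** Stopping study treatment and leaving the study are different events with different consequences for the data. Section 6.8.2 merges them for one trigger, and the sections around it keep them apart. A site that reads 6.8.2 literally would close out a participant whom 7.1.1 and 8.3.1 tell it to keep following.

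The loss would not be random. For most items on the list, the need for the treatment reflects how the participant is doing. The data at stake are SAEs and AESIs to 90 days, survival status, the record of first subsequent anticancer therapy and, in some cases, the scans that would confirm a response or date a progression.

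**Working it through.** This is a comparison of texts. It recomputes no planned figure. The Cohort A figures in substudy 01, section 9.2, reproduce and are unaffected: 8/40 = 20% with a 90% Clopper-Pearson interval of 10.4% to 33.2%, and 1 − 0.95^40 = 87.1% for seeing at least one event with a true rate of 5%.

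**Step 1. Same trigger, different outcome.**

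| Section | Trigger | Effect on study treatment | Effect on follow-up |
|---|---|---|---|
| 6.8.2 | Prohibited treatment needed | Ends | Ends, if read literally |
| 6.8 | Prohibited treatment indicated | May end, or continue by three-way agreement | None stated |
| 7.1.1 | Any permanent stop | Ended | Continues |
| 1.1, 4.1 | Another anticancer therapy started | – | Imaging ends, survival contact continues |
| 8.3.1 | Last dose given | – | SAEs and AESIs to 90 days |

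The closest conflict is between 6.8.2 and 6.8, which address the same event. Section 6.8.2 also sits badly with its own closing statement: if nothing is prohibited in follow-up, needing such a treatment is no reason to end follow-up.

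**Step 2. What a literal reading loses beyond what the plan already gives up.**

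- *New anticancer therapy.* Section 8.1.1 already drops tumor assessment. The best-overall-response window (9.4.2.1) closes there, and DoR (9.4.3.2) and PFS (9.4.3.4) are censored there. The added loss is safety and survival data only.
- *Non-exempt immunosuppressants and live vaccines.* No rule ends imaging for these, so tumor assessments are lost as well. Confirmation requires a second assessment at least 4 weeks after the first (9.4.2.1), so a response awaiting it would not count. A participant without an event would be censored for PFS or DoR at the last valid scan, for a reason that can be linked to prognosis.
- *Tumor-control radiotherapy.* This falls in one group or the other depending on whether it is counted as another anticancer therapy.

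**Step 3. Size.** The documents state no expected rate of removal. The only firm figure is the weight of one participant: 1/40 = 2.5 percentage points of a rate in a cohort of about 40.

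For direction only, assume that 10 of 40 are truly event-free at 6 months and that *m* of the other 30 are removed and censored before any event. The Kaplan-Meier estimate is then 10/(40 − *m*):

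- *m* = 0: 10/40 = 25.0%
- *m* = 1: 10/39 = 25.6%
- *m* = 2: 10/38 = 26.3%

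Under these assumptions the estimate moves upward. Neither the 10 nor the *m* comes from the protocol.

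**The case against.** The strongest reply is that, in context, removal means leaving trial treatment. The prohibition covers only screening and treatment, 6.8.2 says nothing is prohibited afterwards, and the specific rules in 4.1, 7.1.1 and 8.3.1 spell out what happens next. A careful site would follow those. This is very likely the intent, but it does not make the sentence say so. The word used is trial, and 6.8 shows that the authors could write study intervention when they meant it.

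Other parts of the reply stand and limit the point:

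- A reader might infer that participants with the regimen's typical toxicities are the ones removed. Section 6.8.2 exempts steroids and other immunosuppressants given for immune-related events, CRS, ICANS, infusion reactions and life-threatening emergencies, as well as physiologic replacement and brief courses.
- A reader might infer that all scans are lost. For new anticancer therapy they already stop by design.
- A reader might infer a shift of several points in ORR. That needs an assumed removal rate, and responders awaiting confirmation who need a prohibited, non-exempt treatment that is not an anticancer therapy. The documents support neither figure. The ORR denominator is also protected, because the efficacy population (9.3) keeps participants who permanently stopped treatment.
- A reader might infer that 7.2 flatly contradicts 7.1.1. Leaving the study is a separate decision from stopping treatment, and a discretionary clause of this kind is common. Section 7.2 expects its use to be uncommon, encourages those who stop IMP to stay, and separates consent to treatment from consent to follow-up. What remains is an overlap: safety and compliance appear as reasons under both headings, with opposite consequences for follow-up.

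**Conclusion.** The contradiction between 6.8.2 and the sections on concomitant therapy, discontinuation, survival follow-up and event collection is real and in current text. A literal reading ends safety and survival follow-up for participants selected by clinical course. Only for treatments that are neither exempt nor anticancer therapy does it also cost tumor assessments, with possible unconfirmed responses and informative censoring of PFS and DoR. The number affected cannot be derived from the documents and may be small; each participant counts for 2.5 points in a cohort of 40. The conclusion assumes that some sites would act on 6.8.2 as written. The part concerning 7.2 is weaker: it calls for clarification and does not support removing the Investigator's ability to withdraw a participant.

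**What to change.** In 6.8.2, replace the instruction to remove the participant from the trial. The new wording should say that any effect on study intervention is handled under sections 6.8 and 7.1, and that the participant stays in study follow-up per the Schedule of Activities unless consent to follow-up is withdrawn. This leaves the list of prohibited treatments and all treatment decisions as they are.

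In 7.2, reconcile the safety and compliance reasons with 7.1.1 so that stopping treatment is kept distinct from leaving the study. Investigator withdrawal itself can remain.

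The cost is one sentence in 6.8.2 and a clarification in 7.2. The visits, phone contacts and event-collection windows already exist, so no new procedure is needed.
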